8.6 Concomitant Medications

Medications will be coded using the WHO Drug Dictionary. Medications taken during the course of the trial (on or after the first study drug dose and before or on the study termination date) will be considered as concomitant medications. Medications started after the study termination date will not be reported in tables, but will be presented in patient data listings. Concomitant medications used to treat AEs will be differentiated from others.

Concomitant medications will be summarized by preferred term only. To count the number of patients who took a medication, a patient who took the same medication multiple times will only be counted once for that medication. Medications will be tabulated in decreasing order of the total number of patients who took each medication. In addition, the total number of patients to ever take any concomitant medications will be presented.

8.7 Pregnancy test

Any female patients with positive pregnancy test during the study period will be listed by treatment group.

9 OTHER ANALYSES

9.1 Drug Exposure

The total daily dose taken during the study will be summarized with descriptive statistics by treatment group.

9.2 Treatment compliance

Patients will be instructed on how to take the study medication. A medication usage diary card will be provided to the patients by the study staff. Patients will record the number of tablets or volume of oral solution taken, or the volume of injection solution administered and the time of injection. For Ferriprox, compliance will be evaluated monthly by the Investigator or delegate by monthly pill counts or volume of drug returned by the patient. For deferoxamine, compliance will be evaluated by the number of infusions performed, which will be recorded monthly through the use of infusion pumps that keep records of those numbers, and by physical assessment of the infusion sites. Reasons for non-compliance with the treatment will be recorded in the source document and in the eCRFs. Compliance reported in the eCRF will be based on the patient's diary and compliance calculation. If compliance is greater than 100% and the patient reports taking all doses as prescribed, compliance will be reported as 100% in the eCRF.

Compliance $\leq 80\%$ and an over-compliance of $\geq 120\%$ will be reported as a protocol deviation. The number and percent of patients who had compliance $\leq 80\%$ or $\geq 120\%$ during the study will be presented by treatment group.

9.3 Transfusional Iron Input

It is noted that transfusional iron input (mg/kg/day) for the 3 months prior to baseline, which is one of the stratification factors of randomization in this study, has been calculated, for example, as follow:

Assumption: 1 mg iron / 1 mL packed Red Blood Cells (pRBCs)

Type of transfusion	Volume of blood transfused (mL)	Average mean hematocrit of pRBC transfused (%) for the site	If partial or exchange transfusions		Iron in pRBC (volume blood transfused*mean hematocrit transfused – volume blood removed*mean hematocrit removed)
			Volume of blood removed (mL)	Average mean hematocrit of pRBC removed (%) for the site (as we do not collect hematocrit, we use hemoglobin*3 = hematocrit as assumption)	
Simple	1200	65			780
Exchange	1250	65	1016	80	0
Partial exchange	2500	65	1000	80	825
Simple	1000	65			650
				Total iron transfused	2255 mg
				Body weight at baseline	54 kg
				3 months*30.5 days	91.5 days

Hence, transfusional iron input (mg/kg/day) for the 3 months = $2255 \text{ mg} / 54 \text{ kg} / 91.5 \text{ days} = 0.46 \text{ mg/kg/day}$.

Transfusional iron input will be calculated monthly during the study in the same way above. Overall total transfusional iron input (mg/kg/day) during the study will be calculated by summing up monthly transfusional iron input. As the total transfusional iron input depends on the length of time a patient remains in the study, the total transfusional iron input will be divided by the total number of days involved in the months where blood transfusion data was obtained and will be compared between the two treatment groups; the same data will be used for the ANCOVA.

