7.1 Primary Efficacy Endpoint

Primary efficacy endpoint is the change from baseline to Week 52 in LIC. Primary efficacy endpoint will be compared between the two treatment groups using an analysis of covariance (ANCOVA) model including treatment variable as the main factor, and overall average transfusional iron input during the study, baseline LIC, and stratification factors (disease category and transfusional iron input in the 3 months prior to baseline) as covariates. The 96.01% $(1 - \alpha)$, where $\alpha = 0.0399$ based on the Pocock’s α spending function for interim analysis) confidence interval (CI) of the difference (Ferriprox minus deferoxamine) in change of LIC from baseline to Week 52 (i.e., Week 52 minus baseline) between the two treatment groups

will be computed. For the demonstration of non-inferiority, the upper limit of the 96.01% CI should be no more than 2 mg/g dw.

The following SAS codes of MIXED procedure will be used to produce the differences in Least Squares (LS) Mean of change in LIC at Month 6 and Month 12 between Ferriprox and deferoxamine groups and the corresponding 96.01% confidence intervals. In the mixed model, AR (1) (autoregressive of order 1) will be used for the covariance structure, and Kenward and Roger's method will be used to estimate the denominator degrees of freedom (SAS model statement option, DDFM = KR).

```

proc mixed data=LIC;
  class patient treat disease prior_iron month
  model LIC_change = treat overall_iron base_LIC disease prior_iron
    month treat*month / noint solution ddfm=kr;
  repeated month / subject=patient(treat) type=ar(1);
  lsmeans treat*month;
  estimate 'Ferriprox - Deferoxamine at Month 6' treat -1 1
    treat*month -1 0 1 0 / cl alpha=0.0399;
  estimate 'Ferriprox - Deferoxamine at Month 12' treat -1 1
    treat*month 0 -1 0 1 / cl alpha=0.0399;
run;

```

Definition of the variables in the statistical model:

LIC_change : Change in LIC from baseline to Week 5
 treat : Ferriprox or Deferoxamine
 month : Duration of treatment in month
 overall_iron : Overall total transfusional iron input (mg/kg/day) during the study
 base_LIC : LIC at baseline
 disease : Sickle cell disease or other anemias
 prior_iron : transfusional iron input in 3 months prior to baseline (≤ 0.3 mg/kg/day or > 0.3 mg/kg/day)

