7.2 Secondary Efficacy Endpoints

- Change from baseline to Week 52 in patient-reported quality of life (SF-36 or Child Health Questionnaire);
- Change from baseline to Week 52 in cardiac MRI T2*;
- Change from baseline to Week 52 in serum ferritin.
- Detailed information on the statistical analyses of the SF-36 or CHQ data is in a separate SAP prepared by QualityMetric Inc..
- The changes from baseline to Week 52 in cardiac MRI T2* and serum ferritin will be compared between the two treatment groups, using an ANCOVA model including treatment variable as the

main factor, and overall average transfusional iron input during the study, baseline cardiac MRI T2* or serum ferritin, and stratification factors (disease category and transfusional iron input in the 3 months prior to baseline) as covariates. As with LIC, the 96.01% CI of the difference between the two treatment groups will be computed for both cardiac MRI T2* and serum ferritin. The cardiac MRI T2* data will be log-transformed before any statistical evaluation. Since cardiac MRI T2* will be measured at baseline, Week 26, and Week 52 as with LIC, the SAS codes for LIC data, with the exception of baseline MRI T2* instead of baseline LIC being included as the covariate, will be used for cardiac MRI T2* data as well.

- The following SAS codes of MIXED procedure will be used to produce the differences in Least Squares (LS) Mean of change in serum ferritin at Months 3, 6, 9, and 12 between Ferriprox and deferoxamine groups and the corresponding 96.01% confidence intervals.

```
proc mixed data=SF;
  class patient treat disease prior_iron month;
  model SF_change = treat overall_iron base_SF disease prior_iron
    month treat*month /
    noint solution ddfm=kr;
  repeated month / subject=patient(treat) type=ar(1);
  lsmeans treat*month;
  estimate 'Ferriprox - Deferoxamine at Month 3' treat -1 1
    treat*month -1 0 0 0 1 0 0 0 / cl alpha=0.0399;
  estimate 'Ferriprox - Deferoxamine at Month 6' treat -1 1
    treat*month 0 -1 0 0 0 1 0 0 / cl alpha=0.0399;
  estimate 'Ferriprox - Deferoxamine at Month 9' treat -1 1
    treat*month 0 0 -1 0 0 0 1 0 / cl alpha=0.0399;
  estimate 'Ferriprox - Deferoxamine at Month 12' treat -1 1
    treat*month 0 0 0 -1 0 0 0 1 / cl alpha=0.0399;
run;
```

Definition of the variables in the statistical model:

SF_change : Change in SF from baseline to Week 5
 treat : Ferriprox or Deferoxamine
 month : Duration of treatment in month

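### SAP 9.3, followed as written, divides on-study transfusional iron by days twice, so Table 14.5.1 would show 0.0150 instead of 0.456 mg/kg/day at the worked example's rate

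*SAP*

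**What the plan says.** SAP 9.3 sets out the derivation in four steps.

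- A pre-baseline example takes 2255 mg of net iron, a baseline weight of 54 kg and 91.5 days (three months of 30.5 days). Its closing line, which begins "Hence, transfusional iron input (mg/kg/day) for the 3 months", arrives at 0.46 mg/kg/day.
- For the treatment period: "Transfusional iron input will be calculated monthly during the study in the same way above".
- Then: "Overall total transfusional iron input (mg/kg/day) during the study will be calculated by summing up monthly transfusional iron input".
- Then, with the reason "As the total transfusional iron input depends on the length of time a patient remains in the study", the instruction is that "the total transfusional iron input will be divided by the total number of days involved in the months where blood transfusion data was obtained".

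The same section says that the result is compared between the arms and used in the ANCOVA. It therefore fills Table 14.5.1, whose unit is mg/kg/day, and is the iron covariate in the LIC, cardiac T2\* and serum ferritin models.

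The variable does not keep one name. The model text in SAP 7.1 has "overall average transfusional iron input during the study, baseline LIC, and stratification factors" and that in SAP 7.2 has "overall average transfusional iron input during the study, baseline cardiac MRI T2* or serum ferritin". The variable list under the SAS code in 7.1 has "Overall total transfusional iron input (mg/kg/day) during the study", and the list in 7.2 agrees with it. Protocol 11.4.1.3 speaks of total input.

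**The concern.** If each monthly value is obtained as in the example, it is already per day. The label on the sum confirms that reading. Dividing the sum by days again gives a quantity that is no longer in mg/kg/day, although Table 14.5.1 says it is.

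At stake is a reported figure that a reader would set beside Table 14.1.8 (pre-baseline input, same unit) and beside the 0.3 mg/kg/day cut-off used for stratification and dosing. A patient whose transfusion did not change would appear to drop from 0.46 to 0.015. The scale of a covariate in the primary model is affected too.

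A smaller question sits in the same sentence. The days counted could be those of every observed month or only those of months with a transfusion. The schedules (Protocol 18.1 and SAP Table 1) collect transfusion information only where it applies, which leaves room for the second reading.

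**Working it through.** **Inputs.** All come from the SAP 9.3 example: the four transfusion rows, 54 kg, 30.5 days per month and 91.5 days in total. Carrying the example's rate into the study period is an assumption made for illustration, because the SAP does not work an on-study case.

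**1. Reproduce the SAP's figure.**
- Simple: 1200 × 0.65 = 780 mg
- Exchange: 1250 × 0.65 − 1016 × 0.80 = 812.5 − 812.8 = −0.3, shown as 0
- Partial exchange: 2500 × 0.65 − 1000 × 0.80 = 825 mg
- Simple: 1000 × 0.65 = 650 mg
- Total 2255 mg; 2255 / 54 / 91.5 = 0.4564, which rounds to the stated 0.46 mg/kg/day.

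**2. Apply the on-study rule literally**, at the same rate for 12 months of 30.5 days (366 days).
- Each monthly value: 0.4564 mg/kg/day
- Sum: 12 × 0.4564 = 5.477
- Divided by days again: 5.477 / 366 = 0.01496, or 0.0150.

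The spread of transfusions over months does not matter. With the example's three months alone, the monthly values sum to 1.369 however the iron is allotted, and 1.369 / 91.5 = 0.01496.

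**3. Divide once.**
- Monthly amount: 2255 / 54 / 3 = 13.92 mg/kg
- Sum: 12 × 13.92 = 167.04 mg/kg
- 167.04 / 366 = 0.4564 mg/kg/day.

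The ratio of step 3 to step 2 is 30.5, the length of a month. The Table 14.5.1 shell shows one decimal, so 0.0150 would print as 0.0.

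**4. General form.** Let month _i_ have aᵢ mg/kg of iron and dᵢ days. One division gives Σaᵢ / Σdᵢ. The literal rule gives Σ(aᵢ / dᵢ) / Σdᵢ. With every dᵢ = 30.5 the second is exactly the first divided by 30.5. With unequal months the factor lies between the shortest and the longest month, so it is near-constant across patients.

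**5. Effect on the models.** Dividing a covariate by a constant multiplies its coefficient by that constant and leaves the treatment coefficient and its confidence interval unchanged. A check on one artificial data set of 213 patients (treatment, iron, baseline LIC) gave a treatment coefficient of −0.275 with either scaling. The iron coefficient moved from 4.437 to 135.3, and 4.437 × 30.5 = 135.3. The t-test p-value in Table 14.5.1 is likewise unaffected by a constant factor.

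**6. Denominator, taken alone with one division.** Suppose a patient is transfused in _k_ of 12 equal months. Counting only those months gives a rate 12/_k_ times the all-months rate: 1.2 for _k_ = 10, 1.5 for 8, 2 for 6 and 3 for 4. As an illustration, take 500 mg in each of 4 months at 54 kg: 2000 / 54 = 37.04 mg/kg. Over 366 days that is 0.101 mg/kg/day; over 4 × 30.5 = 122 days it is 0.304. The values of _k_ and the 500 mg are assumed. The documents do not give the pattern. Entry requires only one transfusion a year (Protocol 4.2), while Protocol 6.2 describes a regimen close to that of thalassemia major.

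**The case against.** The strongest reply is that nobody meant two divisions. The reason given for dividing is time in study, which makes sense only if the sum is an amount that grows with time. The model text calls the covariate an average, and the table heading is a mean rate. The instruction to follow the example could refer to the net-iron method and stop short of its last step. The slip would also show itself, since a column of 0.0 beside pre-baseline values near 0.46 would prompt a query. All of this stands as evidence of intent. But no sentence in the SAP says that the monthly values stay in mg/kg, and the label on the sum says the opposite. The rule as written yields a wrong number.

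The denominator doubt is also weaker than it first looks. The reason stated in 9.3 favours all observed months, and Protocol 5.1 requires every transfusion during the trial to be recorded, so a month without one is an observed zero. The naming differences are editorial, because 9.3 links the terms by saying that the divided quantity is what enters the ANCOVA. Both are clarifications to make in the same edit.

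A reader might infer that a mis-scaled covariate in the primary model puts the non-inferiority result in doubt. Steps 4 and 5 show otherwise. A reader might also want a power loss attached to the transfused-months reading. The documents give neither the transfusion pattern nor the spread of iron per transfused month, and any such figure depends heavily on both, so none is quoted here.

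**Conclusion.** The concern holds as a minor correction. Followed literally, SAP 9.3 reports 0.0150 where the correct value is 0.456 mg/kg/day, 30.5-fold too small. This rests on 30.5-day months, as in the SAP's example, and on all months being counted. One division was probably intended, so this is a fault in the written rule; the documents do not show that the analysis program contains it.

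The consequence is confined to the values in Table 14.5.1 and the scale of the covariate. The LIC treatment difference, its confidence interval and the non-inferiority decision do not change when the factor is constant, and essentially do not change when month lengths differ slightly.

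Counting only transfused months would be a different kind of error, because 12/_k_ varies between patients. It would overstate individual rates and modestly weaken the covariate adjustment, without bias if transfusion patterns are balanced between the arms. Its size cannot be fixed from the documents, and the SAP's stated reason already points to the other reading.

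**What to change.** In SAP 9.3, replace the on-study rule with one that has a single division:

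- calculate each month's net iron (mg) divided by baseline body weight (kg), as in the example, and keep it in mg/kg;
- sum over all months on study, with transfusion-free months counted as zero;
- divide once by all days in that same period;
- attach the unit mg/kg/day only to the result.

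In the same edit, use the single name _overall average transfusional iron input (mg/kg/day)_ in the text and variable lists of SAP 7.1 and 7.2, in 9.3 and in Table 14.5.1.

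The cost is one or two sentences, one name in a few places, and a check of the derivation program before database lock. No new data are needed.

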14 SUMMARY TABLES AND FIGURES

Summary tables and figures are numbered following ICH structure.

Note: The final numberings for tables and/or figures in the clinical study report can be changed if more tables and/or figures are made in the addition to those in the SAP.

TABLES

14.1 Demographics and Baseline Data

Table 14.1.1 Patient disposition

Table 14.1.2 Number of patients in the efficacy and safety populations

Table 14.1.3 Number of patients by study site

Table 14.1.4 Reasons for not completing the study

Table 14.1.5 Demographics data

Table 14.1.6 Liver iron concentration (LIC), cardiac MRI T2*, serum ferritin at baseline

Table 14.1.7 Prior chelation therapy

Table 14.1.8 Transfusion iron input (mg/kg/day) in the 3 months prior to baseline

Table 14.1.9 Medical history

Table 14.1.10 Vital signs at baseline

Table 14.1.11 Weight and height at baseline

14.2 Efficacy Analyses

Note: Similar tables will be produced for SCD patients only and Non-SCD patients.

14.2.1 LIC

Table 14.2.1.1 LIC at each assessment

Table 14.2.1.2 Change in LIC at each follow-up assessment

Table 14.2.1.3 LS Means of change in LIC from ANCOVA model at each follow-up assessment

Table 14.2.1.4 Trend analysis for LIC over time

14.2.2 Cardiac MRI T2*

Table 14.2.2.1 Cardiac MRI T2* at each assessment

Table 14.2.2.2 Change cardiac MRI T2* at each follow-up assessment

Table 14.2.2.3 LS Means of change in cardiac MRI T2* from ANCOVA model at each follow-up assessment

Table 14.2.2.4 Trend analysis for cardiac MRI T2* over time

14.2.3 Serum Ferritin

Table 14.2.3.1 Serum ferritin at each assessment

Table 14.2.3.2 Change in serum ferritin at each follow-up assessment

Table 14.2.3.3 LS Means of change in serum ferritin from ANCOVA model at each follow-up assessment

Table 14.2.3.4 Trend analysis for serum ferritin over time

14.3 Safety Analyses

Note: Similar tables will be produced for SCD patients only and Non-SCD patients.

14.3.1 Adverse Events

Table 14.3.1.1 Overall summary of adverse events

Table 14.3.1.2 Adverse events

Table 14.3.1.3 Most common adverse events ($\geq 5\%$ in total)

Table 14.3.1.4 Adverse drug reactions

Table 14.3.1.5 Most common adverse drug reactions ($\geq 5\%$ in total)

Table 14.3.1.6 Serious adverse events

Table 14.3.1.7 Serious adverse drug reactions

Table 14.3.1.8 Adverse events by causality

14.3.2 Vital Signs

Table 14.3.2.1 Temperature at each assessment

Table 14.3.2.2 Change in temperature from baseline to each follow-up assessment

Note: Similar tables will be produced for resting heart rate, respiration, systolic blood pressure, and diastolic blood pressure.

14.3.3 Weight and Height

Table 14.3.3.1 Weight at each assessment

Table 14.3.3.2 Change in weight from baseline to last assessment

Table 14.3.3.1 Height at each assessment

Table 14.3.3.2 Change in height from baseline to last assessment

14.3.4 Concomitant Medications

Table 14.3.4.1 Concomitant medications

14.3.5 12-Lead ECG

Table 14.3.5.1 Heart rate of 12-Lead ECG at each assessment

Table 14.3.5.2 Change in heart rate of 12-Lead ECG from baseline to each follow-up assessment

Note: Similar tables will be produced for PR, QRS, QT, QTcF, and QTcB.

Table 14.3.5.3 Shift table for clinically significant abnormality for 12-Lead ECG: Feriprox group

Table 14.3.5.4 Shift table for clinically significant abnormality for 12-Lead ECG: Deferoxaome group

14.3.6 Laboratory Data

14.3.6.1 Hematology

Table 14.3.6.1.1 Hemoglobin at each assessment

Table 14.3.6.1.2 Change in hemoglobin from baseline to each follow-up assessment

Table 14.3.6.1.3 Shift table for hemoglobin in abnormal range at baseline vs. last assessment: Feriprox group

Table 14.3.6.1.4 Shift table for hemoglobin in abnormal range at baseline vs. last assessment:

Deferoxamine group

Note: Similar tables will be produced for total white blood cell (WBC), absolute neutrophil count (ANC), and platelets.

14.3.6.2 Biochemistry

Table 14.3.6.2.1 Total protein at each assessment

Table 14.3.6.2.2 Change in total protein from baseline to each follow-up assessment

Table 14.3.6.2.3 Shift table for total protein in abnormal range at baseline vs. last assessment: Feriprox group

Table 14.3.6.2.4 Shift table for total protein in abnormal range at baseline vs. last assessment:

Deferoxamine group

Note: Similar tables will be produced for GGT, lactate dehydrogenase (LDH), sodium, potassium, chloride, glucose (fasting at screening visit only), total, direct and indirect bilirubin, AST, ALT, albumin; blood urea nitrogen, calcium, creatinine, uric acid, alkaline phosphatase, and amylase.

14.3.6.3 Serology

Table 14.3.6.3.1 HIV at each assessment

Note: Similar tables will be produced for Hepatitis B and C.

14.3.7 Pregnancy test

Table 14.3.7.1 List of patients with positive pregnancy test during the study

14.4 Treatment compliance

Table 14.4.1 Treatment compliance at each visit

14.5 Transfusion information

Table 14.5.1 Mean transfusional iron input (mg/kg/day) during the study

14.6 Total daily dose

Table 14.6.1 Summary of total daily dose

FIGURES

14.2 Efficacy

Figure 14.2.1 Mean line graph for LIC over time

Figure 14.2.2 Mean line graph for cardiac MRI T2* over time

Figure 14.2.3 Mean line graph for serum ferritin over time

Figure 14.2.4 Bar graph for the change in LIC from baseline to the end of study

Figure 14.2.5 Bar graph for the change in cardiac MRI T2* from baseline to the end of study

Figure 14.2.6 Bar graph for the change in serum ferritin from baseline to the end of study

14.3 Safety

14.3.1 Hematology

Figure 14.3.1.1 Mean line graph for hemoglobin over visit

Figure 14.3.1.2 Proportion of patients with abnormal hemoglobin at each assessment

Note: Similar graphs will be produced for total white blood cell (WBC), absolute neutrophil count (ANC), and platelets.

14.3.2 Biochemistry

Figure 14.3.2.1 Mean line graph for total protein over visit

Figure 14.3.2.2 Proportion of patients with abnormal total protein at each assessment

Note: Similar tables will be produced for GGT, lactate dehydrogenase (LDH), sodium, potassium, chloride, glucose (fasting at screening visit only), total, direct and indirect bilirubin, AST, ALT, albumin; blood urea nitrogen, calcium, creatinine, uric acid, alkaline phosphatase, and amylase.

16 DATA LISTINGS

Data listings are numbered following ICH structure.

Note: The final numberings for patient data listings in the clinical study report can be changed if more patient data listings are made in the addition to those in the SAP.

